#### **7.4.3 Criteria to Resume Treatment**

Delayed doses of study treatment should be administered as soon as the participant meets criteria to resume treatment. If a dose has been delayed, the participant should not wait until the next scheduled dosing date.

Participants may resume study treatment when the drug-related AEs resolve to Grade  $\leq 1$  or baseline value, with the following exceptions:

- Participants may resume treatment in the presence of Grade 2 fatigue.
- Participants who have not experienced a Grade 3 drug-related skin AE may resume treatment in the presence of Grade 2 skin toxicity.
- For participants with Grade 2 AST, ALT, and/or TBili abnormalities, dosing may resume when laboratory values return to baseline and management with corticosteroids, if needed, has been completed.
- Drug-related pulmonary toxicity, diarrhea, or colitis must have resolved to baseline before treatment is resumed. Participants with persistent Grade 1 pneumonitis after completion of a steroid taper over at least 1 month may be eligible for retreatment if discussed with and approved by the BMS medical monitor or designee.
- Participants with drug-related endocrinopathies that are adequately controlled with only physiologic hormone replacement may resume treatment.

#### **7.4.4 Criteria for Treatment Discontinuation**

The assessment for discontinuation of nivolumab should be made separately from the assessment made for discontinuation of ipilimumab. Although there is an overlap among the discontinuation criteria, if the discontinuation criteria are met for ipilimumab but not for nivolumab, treatment with nivolumab may continue if ipilimumab is discontinued.

If a participant meets the criteria for discontinuation and the investigator is unable to determine whether the event is related to both or one study drug, the participant should discontinue both nivolumab and ipilimumab and be taken off the treatment phase of the study.

For participants who discontinue study treatment without documented disease progression, tumor and other assessments per protocol-defined schedule should be followed until initiation of another anti-cancer treatment, withdrawal of consent, or death, whichever occurs first.

#### **7.4.4.1 Nivolumab Dose Discontinuation**

Nivolumab treatment should be permanently discontinued for the following:

- Any Grade 2 drug-related uveitis, eye pain or blurred vision that does not respond to topical therapy and does not improve to Grade 1 severity within the retreatment period OR requires systemic treatment
- Any Grade 3 non-skin, drug-related AE lasting  $> 7$  days or recurs, with the following exceptions for laboratory abnormalities, neurologic toxicity, drug-related uveitis, pneumonitis, bronchospasm, hypersensitivity reactions, infusion reactions, and endocrinopathies:
  - Grade 3 drug-related neurologic toxicity, uveitis, pneumonitis, bronchospasm, myocarditis, hypersensitivity reaction, or infusion reaction of any duration requires discontinuation
  - Grade 3 drug-related endocrinopathies, adequately controlled with only physiologic hormone replacement do not require discontinuation. Adrenal insufficiency requires discontinuation regardless of control with hormone replacement.
  - Grade 3 drug-related laboratory abnormalities do not require treatment discontinuation except:
    - ◆ Grade 3 drug-related thrombocytopenia  $> 7$  days or associated with bleeding requires discontinuation
    - ◆ Grade  $\geq 3$  drug-related AST, ALT, or TBili requires discontinuation\*
    - ◆ Concurrent AST or ALT  $> 3 \times$  ULN and TBili  $> 2 \times$  ULN
- \*In most cases of Grade 3 AST or ALT elevation, study treatment will be permanently discontinued. If the investigator determines a possible favorable benefit/risk ratio that warrants continuation of study treatment, a discussion between the investigator and the BMS medical monitor/designee must occur.
- Any Grade 4 drug-related AE or laboratory abnormality (including but not limited to creatinine, AST, ALT, or TBili), except for the following events, which do not require discontinuation:
  - Grade 4 neutropenia  $\leq 7$  days
  - Grade 4 lymphopenia or leukopenia or asymptomatic amylase or lipase
  - Isolated Grade 4 electrolyte imbalances/abnormalities that are not associated with clinical sequelae and are corrected with supplementation/appropriate management within 72 hours of their onset
  - Grade 4 drug-related endocrinopathy AEs, such as, hyper- or hypothyroidism, or glucose intolerance, which resolve or are adequately controlled with physiologic hormone replacement (eg, corticosteroids, thyroid hormones) or glucose-controlling agents, respectively, may not require discontinuation after discussion with and approval from the BMS medical monitor.
- Any event that leads to delay in dosing lasting  $> 10$  weeks from the previous dose requires discontinuation, with the following exceptions:
  - Dosing delays to allow for prolonged steroid tapers to manage drug-related AEs
  - Dosing delays lasting  $> 10$  weeks from the previous dose that occur for non-drug-related reasons, if approved by the BMS medical monitor (or designee)

Prior to re-initiating treatment in a participant with a dosing delay lasting > 10 weeks, the BMS medical monitor (or designee) must be consulted. Tumor and other assessments should continue per protocol even if dosing is delayed. Periodic study visits to assess safety and laboratory studies should also continue Q3W during induction, Q4W during maintenance, or more frequently if clinically indicated during such dosing delays.

Any AE, laboratory abnormality, or intercurrent illness which, in the judgment of the Investigator, presents a substantial clinical risk to the participant with continued nivolumab dosing.

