#### **7.4.4.2 *Ipilimumab Dose Discontinuation***

Ipilimumab treatment should be permanently discontinued for the following:

- Any Grade 2 drug-related uveitis, eye pain, or blurred vision that does not respond to topical therapy and does not improve to Grade 1 severity within the retreatment period OR requires systemic treatment
- Any Grade 3 non-skin, drug-related AE lasting > 7 days, or recurs, with the following exceptions for laboratory abnormalities, diarrhea, colitis, neurologic toxicity, drug-related uveitis, pneumonitis, bronchospasm, hypersensitivity reactions, infusion reactions, and endocrinopathies:
  - Grade 3 drug-related diarrhea, colitis, neurologic toxicity, uveitis, pneumonitis, bronchospasm, myocarditis, hypersensitivity reaction, or infusion reaction of any duration requires discontinuation.
  - Grade 3 drug-related endocrinopathies adequately controlled with only physiologic hormone replacement do not require discontinuation. Adrenal insufficiency requires discontinuation regardless of control with hormone replacement.
  - Grade 3 drug-related laboratory abnormalities do not require treatment discontinuation except:
    - ◆ Grade 3 drug-related thrombocytopenia > 7 days or associated with bleeding requires discontinuation
    - ◆ Any drug-related liver function test abnormality that meets the following criteria require discontinuation:
      - Grade  $\geq$  3 drug-related AST, ALT, or TBili requires discontinuation\*
      - Concurrent AST or ALT > 3 $\times$  ULN and TBili > 2 $\times$  ULN

\*In most cases of Grade 3 AST or ALT elevation, study treatment will be permanently discontinued. If the investigator determines a possible favorable benefit/risk ratio that warrants continuation of study treatment, a discussion between the investigator and the BMS medical monitor/designee must occur.

- Any Grade 4 drug-related AE or laboratory abnormality (including but not limited to creatinine, AST, ALT, and TBili), except for the following events, which do not require discontinuation:
  - Grade 4 neutropenia  $\leq$  7 days
  - Grade 4 lymphopenia or leukopenia or asymptomatic amylase or lipase

- Isolated Grade 4 electrolyte imbalances/abnormalities that are not associated with clinical sequelae and are corrected with supplementation/appropriate management within 72 hours of their onset

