- Grade 4 drug-related endocrinopathy AEs, such as hyper- or hypothyroidism or glucose intolerance, which resolve or are adequately controlled with physiologic hormone replacement (eg, corticosteroids, thyroid hormones) or glucose-controlling agents, respectively, may not require discontinuation after discussion with and approval from the BMS medical monitor.
- Any event that leads to delay in dosing lasting > 8 weeks from the previous dose requires discontinuation, with the following exceptions:
  - Dosing delays to allow for prolonged steroid tapers to manage drug-related AEs are allowed.
  - Dosing delays lasting > 8 weeks from the previous dose that occur for non-drug-related reasons may be allowed if approved by the BMS medical monitor (or designee).

Prior to re-initiating treatment in a participant with a dosing delay lasting > 8 weeks, the BMS medical monitor (or designee) must be consulted. Tumor and other assessments should continue per protocol even if dosing is delayed. Periodic study visits to assess safety and laboratory studies should also continue Q3W during induction, Q4W during maintenance, or more frequently if clinically indicated during such dosing delays.

Any AE, laboratory abnormality, or intercurrent illness that, in the judgment of the investigator, presents a substantial clinical risk to the participant with continued ipilimumab dosing.

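### The Grade 4 endocrinopathy exception for nivolumab and ipilimumab does not exclude adrenal insufficiency, so it cannot be squared with the adrenal insufficiency stop placed under Grade 3

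*Combined protocol and SAP*

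**What the plan says.** Sections 7.4.4.1 (nivolumab) and 7.4.4.2 (ipilimumab) are built the same way on this point.

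- **Grade 3.** A sub-bullet under the Grade 3 non-skin rule lets endocrinopathies continue if hormone replacement alone controls them. It then adds: "Adrenal insufficiency requires discontinuation regardless of control with hormone replacement". That added sentence carries no grade.
- **Grade 4.** The default is a permanent stop for "Any Grade 4 drug-related AE or laboratory abnormality", followed by a short list of exceptions. One of them, for nivolumab, covers "Grade 4 drug-related endocrinopathy AEs, such as, hyper- or hypothyroidism, or glucose intolerance, which resolve or are adequately controlled with physiologic hormone replacement" and continues "eg, corticosteroids, thyroid hormones) or glucose-controlling agents, respectively, may not require discontinuation after discussion with and approval from the BMS medical monitor". The ipilimumab section opens its exception in nearly identical words: "Grade 4 drug-related endocrinopathy AEs, such as hyper- or hypothyroidism or glucose intolerance, which resolve or are adequately controlled with physiologic hormone replacement". Neither mentions adrenal insufficiency.

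Section 8.1 makes the criteria of section 7.4.4 reasons for which a participant must come off study drug, and section 9 rules out waivers. At entry, sections 5.1 and 6.2 exclude people with a prior event that met the 7.4.4 criteria, but make an exception for a history of adrenal insufficiency controlled by hormone replacement.

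**The concern.** These are participant safety rules, and one would expect the stop to be at least as strict at Grade 4 as at Grade 3. For adrenal insufficiency the text does not secure that. A medical monitor asked about a controlled Grade 4 case could point to the exception and approve further dosing. An investigator could point to the adrenal sentence and say the participant must stop. Sites could therefore handle the same event differently, and the protocol gives no way to say which of them followed it.

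**Working it through.** No arithmetic decides this point. The check is to set the rules side by side and apply each reading to one case: drug-related adrenal insufficiency, adequately controlled by hormone replacement.

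**Step 1: does the Grade 4 exception reach adrenal insufficiency?** Its examples (thyroid disorders, glucose intolerance) are introduced as illustrations, so the list is open. It names corticosteroids among the replacement agents. Neither a thyroid disorder nor glucose intolerance is what steroid replacement is for, whereas sections 6.2 and 7.7.3 speak of adrenal replacement steroids. The wording therefore fits adrenal insufficiency, although it does not name it.

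**Step 2: apply the two readings.** The result is the same for each drug.

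| Reading of the adrenal sentence | Controlled, Grade 3 | Controlled, Grade 4 | Result |
|---|---|---|---|
| By placement (Grade 3 only) | Must stop | May continue if the monitor approves | The higher grade has the looser rule |
| All grades | Must stop | Must stop under one sentence; may continue under the exception | The two rules contradict each other |

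**Step 3: which reading does the text favour?** For placement: the sentence sits under a Grade 3 heading, and in the same group of sub-bullets the liver-test stop is written as Grade 3 or higher, so the authors had a way to carry a stop upward and did not use it here. For all grades: the sentence before it specifies Grade 3 and this one does not. The text does not settle the matter.

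**Step 4: does another section settle it?** Section 7.4.3 lets hormone-controlled endocrinopathies resume after a delay and does not exclude adrenal insufficiency either. It governs delayed doses, so it does not decide when a stop is permanent. Section 8.1 only refers back to 7.4.4. The endocrinopathy algorithm in Appendix 5 is a figure that is not shown, and the appendix describes itself as guidance.

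**Step 5: is this a general pattern?** No. The other named Grade 3 stops for nivolumab ("Grade 3 drug-related neurologic toxicity, uveitis, pneumonitis, bronchospasm, myocarditis, hypersensitivity reaction, or infusion reaction of any duration requires discontinuation") and for ipilimumab ("Grade 3 drug-related diarrhea, colitis, neurologic toxicity, uveitis, pneumonitis, bronchospasm, myocarditis, hypersensitivity reaction, or infusion reaction of any duration requires discontinuation") fall in none of the Grade 4 exceptions, which cover brief neutropenia, certain blood-count and pancreatic-enzyme findings, corrected electrolytes, and endocrinopathy. The thrombocytopenia and liver-test stops do not fall in them either. For liver enzymes the discretion lies at the lower grade: the footnote that begins "In most cases of Grade 3 AST or ALT elevation, study treatment will be permanently discontinued" opens a discussion with the monitor for Grade 3 AST or ALT. This suggests that an exclusion was overlooked, though it does not prove it.

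**Step 6: scale.** The documents give no adrenal insufficiency rate. The nearest figure is in Table 3.2.6.4-2: drug-related endocrine events of Grade 3 or 4 in 38 of 547 first-line patients on the combination (38 / 547 = 6.9%). If that rate carried over to about 96 participants, which is an assumption, 96 × 38 / 547 ≈ 6.7 would have such an event. That covers all endocrine conditions and both grades; Grade 4 adrenal insufficiency would be some unknown part of it, possibly none.

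**The case against.** The strongest reply is that the adrenal sentence has no grade because none was meant. On that view it is a specific, mandatory stop for one named condition, and it overrides a general, permissive exception that does not name that condition. Nothing would then be inverted. This is a fair reading, and it is why the inversion cannot be stated as fact. It does not make the edit unnecessary: the reader must still choose between two sentences that give opposite answers, and the protocol has no rule of precedence.

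The safeguards also count. The Grade 4 default is a stop. The exception is permissive, requires resolution or adequate control, and needs discussion with and approval from the medical monitor. The investigator can also stop either drug when continued dosing looks too dangerous. An unapproved Grade 4 case therefore stops. All of this stands, and it keeps the point minor.

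Third, the entry exception shows that the sponsor accepts giving both drugs to people whose past adrenal insufficiency is controlled. This stands as a limit: the documents do not show that dosing under hormone control is harmful, and one could reconcile the rules by relaxing Grade 3 instead. But the entry exception concerns history, while the on-study stop remains in the current text. Following that explicit stop is the smaller change.

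Finally, the algorithm figure may address severe adrenal events. That cannot be checked here.

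**Conclusion.** The point holds as a missing cross-exclusion. For each drug, the adrenal insufficiency stop and the Grade 4 endocrinopathy exception give either a looser rule at the higher grade or a direct contradiction, depending on how an ungraded sentence is read. It affects one condition at one grade, in two bullets.

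A reader might infer more: that the protocol expressly permits dosing after Grade 4 adrenal insufficiency, or that the more severe event definitely gets the looser rule. The documents do not support that. The adrenal sentence states no grade, the exception does not name adrenal insufficiency, and continuation is never automatic. Nor do they support a claim that participants would be harmed, given whom the protocol admits.

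The conclusion rests on two assumptions: that the unseen algorithm figure does not resolve the conflict, and that controlled Grade 4 cases are rare. Sample size, type I error, power and the planned analyses are untouched. Severity is minor.

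**What to change.** In the Grade 4 endocrinopathy bullet of both 7.4.4.1 and 7.4.4.2, insert after *endocrinopathy AEs*: *(except adrenal insufficiency, which requires discontinuation)*. That is two insertions, one per drug, in the next amendment.

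Leave the existing adrenal sentence unchanged. Rewriting it as a rule for drug-related Grade 3 or 4 events could narrow a stop that now has no stated grade. Whether that sentence also reaches lower grades, where the delay and resume rules of 7.4.2 and 7.4.3 apply, stays as open as it is now; the insertion settles Grade 4 only.

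The cost is that the medical monitor loses discretion in rare controlled Grade 4 cases, discretion that the plan already withholds at Grade 3. Data collection and analysis do not change. If the sponsor wants to keep that discretion, it should say so and explain why Grade 3 is treated more strictly.

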#### **7.4.4.2 *Ipilimumab Dose Discontinuation***

Ipilimumab treatment should be permanently discontinued for the following:

- Any Grade 2 drug-related uveitis, eye pain, or blurred vision that does not respond to topical therapy and does not improve to Grade 1 severity within the retreatment period OR requires systemic treatment
- Any Grade 3 non-skin, drug-related AE lasting > 7 days, or recurs, with the following exceptions for laboratory abnormalities, diarrhea, colitis, neurologic toxicity, drug-related uveitis, pneumonitis, bronchospasm, hypersensitivity reactions, infusion reactions, and endocrinopathies:
  - Grade 3 drug-related diarrhea, colitis, neurologic toxicity, uveitis, pneumonitis, bronchospasm, myocarditis, hypersensitivity reaction, or infusion reaction of any duration requires discontinuation.
  - Grade 3 drug-related endocrinopathies adequately controlled with only physiologic hormone replacement do not require discontinuation. Adrenal insufficiency requires discontinuation regardless of control with hormone replacement.
  - Grade 3 drug-related laboratory abnormalities do not require treatment discontinuation except:
    - ◆ Grade 3 drug-related thrombocytopenia > 7 days or associated with bleeding requires discontinuation
    - ◆ Any drug-related liver function test abnormality that meets the following criteria require discontinuation:
      - Grade  $\geq$  3 drug-related AST, ALT, or TBili requires discontinuation\*
      - Concurrent AST or ALT > 3 $\times$  ULN and TBili > 2 $\times$  ULN

\*In most cases of Grade 3 AST or ALT elevation, study treatment will be permanently discontinued. If the investigator determines a possible favorable benefit/risk ratio that warrants continuation of study treatment, a discussion between the investigator and the BMS medical monitor/designee must occur.

- Any Grade 4 drug-related AE or laboratory abnormality (including but not limited to creatinine, AST, ALT, and TBili), except for the following events, which do not require discontinuation:
  - Grade 4 neutropenia  $\leq$  7 days
  - Grade 4 lymphopenia or leukopenia or asymptomatic amylase or lipase

- Isolated Grade 4 electrolyte imbalances/abnormalities that are not associated with clinical sequelae and are corrected with supplementation/appropriate management within 72 hours of their onset
- Grade 4 drug-related endocrinopathy AEs, such as hyper- or hypothyroidism or glucose intolerance, which resolve or are adequately controlled with physiologic hormone replacement (eg, corticosteroids, thyroid hormones) or glucose-controlling agents, respectively, may not require discontinuation after discussion with and approval from the BMS medical monitor.
- Any event that leads to delay in dosing lasting > 8 weeks from the previous dose requires discontinuation, with the following exceptions:
  - Dosing delays to allow for prolonged steroid tapers to manage drug-related AEs are allowed.
  - Dosing delays lasting > 8 weeks from the previous dose that occur for non-drug-related reasons may be allowed if approved by the BMS medical monitor (or designee).

Prior to re-initiating treatment in a participant with a dosing delay lasting > 8 weeks, the BMS medical monitor (or designee) must be consulted. Tumor and other assessments should continue per protocol even if dosing is delayed. Periodic study visits to assess safety and laboratory studies should also continue Q3W during induction, Q4W during maintenance, or more frequently if clinically indicated during such dosing delays.

Any AE, laboratory abnormality, or intercurrent illness that, in the judgment of the investigator, presents a substantial clinical risk to the participant with continued ipilimumab dosing.

#### **7.4.5      *Treatment of Infusion-related Reactions***

Because nivolumab and ipilimumab contain only human immunoglobulin protein sequences, they are unlikely to be immunogenic and induce infusion or hypersensitivity reactions. However, if such a reaction were to occur, it might manifest with fever, chills, rigors, headache, rash, pruritus, arthralgias, hypo- or hypertension, bronchospasm, or other allergic-like reactions. Regardless of whether or not the event is attributed to the study drugs, all Grade 3 or 4 infusion reactions should be reported within 24 hours to the BMS medical monitor or designee and reported as an SAE if criteria are met. Infusion reactions should be graded according to NCI CTCAE [version 5.0] guidelines.

Treatment recommendations are provided below and may be modified based on local treatment standards and guidelines as appropriate:

**For Grade 1 symptoms** - mild reaction; infusion interruption not indicated; intervention not indicated:

- Remain at bedside and monitor participant until recovery from symptoms. The following prophylactic premedications are recommended for future infusions: diphenhydramine 50 mg (or equivalent) and/or paracetamol (acetaminophen) 325 mg to 1,000 mg at least 30 minutes before additional study drug administrations.

**For Grade 2 symptoms** - moderate reaction; requires therapy or infusion interruption but responds promptly to symptomatic treatment (eg, antihistamines, non-steroidal anti-inflammatory drugs, narcotics, corticosteroids, bronchodilators, and IV fluids); prophylactic medications indicated for  $\geq 24$  hours:

- Stop the study drug infusion, begin an IV infusion of normal saline, and treat the participant with diphenhydramine 50 mg IV (or equivalent) and/or paracetamol (acetaminophen) 325 mg to 1,000 mg; remain at bedside and monitor participant until resolution of symptoms. Corticosteroid or bronchodilator therapy may also be administered as appropriate. If the infusion is interrupted, then restart the infusion at 50% of the original infusion rate when symptoms resolve; if no further complications ensue after 30 minutes, the rate may be increased to 100% of the original infusion rate. Monitor participant closely. If symptoms recur, then no further study drug will be administered at that visit. Administer diphenhydramine 50 mg IV, and remain at bedside and monitor the participant until resolution of symptoms. The amount of study drug infused must be recorded on the electronic case report form (eCRF).
- The following prophylactic premedications are recommended for future infusions: diphenhydramine 50 mg (or equivalent) and/or paracetamol (acetaminophen) 325 mg to 1,000 mg should be administered at least 30 minutes before additional study drug administrations. If necessary, corticosteroids (recommended dose: up to 25 mg of IV hydrocortisone or equivalent) may be used.

**For Grade 3 or Grade 4 symptoms** - severe reaction, Grade 3: prolonged (ie, not rapidly responsive to symptomatic medication and/or brief interruption of infusion); recurrence of symptoms following initial improvement; hospitalization indicated for other clinical sequelae (eg, renal impairment, pulmonary infiltrates). Grade 4: life threatening; pressor or ventilatory support indicated:

- Immediately discontinue infusion of study drug. Begin an IV infusion of normal saline and treat the participant as follows. Recommend bronchodilators, epinephrine 0.2 mg to 1 mg of a 1:1,000 solution for subcutaneous administration or 0.1 mg to 0.25 mg of a 1:10,000 solution injected slowly for IV administration, and/or diphenhydramine 50 mg IV with methylprednisolone 100 mg IV (or equivalent), as needed. Participant should be monitored until the investigator is comfortable that the symptoms will not recur. Study drug will be permanently discontinued. Investigators should follow their institutional guidelines for the treatment of anaphylaxis. Remain at bedside and monitor participant until recovery from symptoms. In the case of late-occurring hypersensitivity symptoms (eg, appearance of a localized or generalized pruritus within 1 week after treatment), symptomatic treatment may be given (eg, oral antihistamine or corticosteroids).

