## 7.1 Treatments Administered

Treatments should be administered according to [Table 7.1-1](#).

Dosing calculations should be based on the body weight assessed at baseline. It is not necessary to recalculate subsequent doses if the participant weight is within 10% of the weight used to calculate the previous dose. All doses should be rounded up or to the nearest milligram per institutional standard.

When study treatments (nivolumab and ipilimumab) are to be administered on the same day, nivolumab is to be administered first. Nivolumab infusion must be promptly followed by a flush of diluent to clear the line of nivolumab before starting the ipilimumab infusion. The second infusion will always be the ipilimumab study treatment and will start after the infusion line has been flushed, the filters have been changed, and the participant has been observed to ensure no infusion reaction has occurred.

There will be no dose increases or reductions of nivolumab allowed. Participants may be dosed no less than 19 days from the previous dose during Q3W cycles. For Q4W dosing cycles, participants may be dosed within a  $\pm$  3-day window. Premedications are not recommended for the first dose of nivolumab.

Participants should be carefully monitored for infusion reactions during nivolumab administration. If an acute infusion reaction is noted, participants should be managed according to [Section 7.4.5](#).

Doses of nivolumab may be interrupted, delayed, or discontinued depending on how well the participant tolerates the treatment. Dosing visits are not skipped, only delayed.

Treatment should be continued until disease progression or unacceptable toxicity, with a maximum nivolumab treatment of 24 months from the first dose in Cycle 1.

Nivolumab injection, 100 mg/10 mL (10 mg/mL) is to be administered as a 30-minute IV infusion through a 0.2- $\mu$ m to 1.2- $\mu$ m pore size, low-protein binding in-line filter at the protocol-specified doses. It is not to be administered as an IV push or bolus injection. For instructions on storage, preparation, and administration of nivolumab, please refer to the current IB and/or pharmacy manual. Care must be taken to ensure sterility of the prepared solution, as the product does not contain any antimicrobial preservative or bacteriostatic agent.

For instructions on storage, preparation, and administration of ipilimumab, please refer to the current IB and/or pharmacy manual.

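### Section 7.4.5 gives two dispositions for an infusion reaction that resolves, is restarted and recurs: the Grade 2 text stops drug for that visit, while the Grade 3 text covers the same course and ends treatment

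*Combined protocol and SAP*

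**What the plan says.** Section 7.1 points staff to Section 7.4.5 during an acute event: "If an acute infusion reaction is noted, participants should be managed according to" that section.

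For a Grade 2 reaction, Section 7.4.5 has the infusion stopped and the symptoms treated. If the infusion was interrupted, staff are to "restart the infusion at 50% of the original infusion rate when symptoms resolve". Then: "If symptoms recur, then no further study drug will be administered at that visit". The recurrence is treated as follows: "Administer diphenhydramine 50 mg IV, and remain at bedside and monitor the participant until resolution of symptoms". The next bullet begins "The following prophylactic premedications are recommended for future infusions" and draws no line between participants whose symptoms recurred and those whose symptoms did not.

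The Grade 3 description in the same section includes "recurrence of symptoms following initial improvement; hospitalization indicated for other clinical sequelae". The action under the Grade 3 or 4 paragraph is permanent discontinuation. Three other places bear on that grade:

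- Sections 7.4.4.1 and 7.4.4.2 require nivolumab and ipilimumab respectively to be stopped for a drug-related Grade 3 infusion reaction, however short.
- Section 8.1 makes the Section 7.4.4 criteria mandatory reasons to stop.
- The opening of Section 7.4.5 asks for every Grade 3 or 4 infusion reaction to be reported to the medical monitor within 24 hours, whether or not it is attributed to study drug.

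**The concern.** Both texts fit the same sequence of events but lead to different next steps. Staff who stay in the Grade 2 bullet would withhold drug for the day and could reasonably plan a premedicated next dose. Staff who read on to the Grade 3 description would end treatment and report within 24 hours.

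Two errors are possible: re-exposing a participant whom the stopping rule removes, and missing the 24-hour report. Sites in a multicenter study could also handle identical events differently. The issue is individual safety and consistent conduct. It does not touch the disease control rate, the sample size, the type I error or the Stage 1 rule.

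**Working it through.** **Tracing one course through the text.** The course is: reaction, infusion stopped, symptoms resolve, restart at 50% rate, symptoms recur.

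| Question | Grade 2 bullets, 7.4.5 | Grade 3 text, 7.4.5, with 7.4.4 and 8.1 |
|---|---|---|
| Does the course fit? | Yes; it is described step by step | Yes; resolution is an initial improvement, and recurrence follows it |
| Drug that day | None further at that visit | Infusion stopped at once |
| Later dosing | Premedication advised; recurrence not excluded | Permanent discontinuation |
| 24-hour report | Not mentioned | Asked for |

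The first two rows are compatible. The conflict lies in the last two, and no sentence in Section 7.4.5 says whether a recurrence after restart stays Grade 2 or becomes Grade 3.

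Acute treatment is not where the texts diverge. The Grade 2 bullet already says "Corticosteroid or bronchodilator therapy may also be administered as appropriate", and the Grade 3 or 4 list is discretionary: "and/or diphenhydramine 50 mg IV with methylprednisolone 100 mg IV (or equivalent), as needed".

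**Which text should prevail.** Section 7.4.5 introduces its treatment text as recommendations open to local modification. Section 7.4.4 has no such allowance. It lists exceptions where they are intended, for example controlled endocrinopathies, and none covers a recurring infusion reaction. Read together, the stopping criteria should govern a reaction graded 3.

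**How often.** The plan gives no figure for this event, so there is nothing to reproduce. The inputs are:

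- Drug-related hypersensitivity/infusion reactions, nivolumab plus ipilimumab, Table 3.2.6.4-2: 22 of 547 any grade, 0 of 547 Grade 3-4 (previously untreated patients, CTC version 4.0).
- Planned participants, Section 5.2: about 96 enrolled for 80 response-evaluable.
- Share of reactions that recur on restart: not in the documents; assumed 5% to 25%.

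Reaction rate: 22/547 = 4.02%; exact (Clopper-Pearson) 95% CI 2.54% to 6.03%.

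Expected reactions = N × rate. For N = 96: 96 × 0.0402 = 3.86 (96 × 0.0254 = 2.44 to 96 × 0.0603 = 5.79).

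Expected recurrences = reactions × assumed share:

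- Point estimate: 3.86 × 0.05 = 0.19 to 3.86 × 0.25 = 0.97.
- Across the CI limits: 2.44 × 0.05 = 0.12 to 5.79 × 0.25 = 1.45.

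Only treated participants are at risk, and Section 10.2 counts anyone consented and registered as enrolled. Taking the 80 response-evaluable participants instead: 80 × 0.0402 = 3.22, giving 3.22 × 0.05 = 0.16 to 3.22 × 0.25 = 0.80.

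The inputs lean high. The 22 events pool hypersensitivity with infusion reactions. They also include Grade 1 events, for which Section 7.4.5 calls for no interruption and so no restart. The rate in participants already exposed to both drugs is not given; it may be lower, because Section 6.2 excludes a known severe hypersensitivity reaction to any monoclonal antibody.

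**The case against.** The best defence is that the two texts do not strictly contradict each other. Stopping drug for the visit is compatible with never giving it again. Grade decides which paragraph applies, and grading is deferred to CTCAE version 5.0. Once the event is called Grade 3, Sections 7.4.5, 7.4.4 and 8.1 agree. The premedication bullet also has an ordinary use, in Grade 2 reactions that did not recur. This stands as far as it goes: a reader might infer that the protocol orders re-dosing after a recurrence, and it does not. But the deferral does not explain why the Grade 2 bullet carries its own recurrence instruction when the printed Grade 3 description also covers recurrence.

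A second argument is that Grade 3 may mean relapse after partial improvement, whereas the Grade 2 restart requires full resolution. That reading is possible, but the protocol does not state it, so the sponsor should say if it is intended.

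Third, there are backstops. Section 9 requires immediate safety concerns to be discussed with the sponsor at once, Sections 7.4.4.1 and 7.4.4.2 allow stopping on investigator judgement, and Section 7.1 requires observation for a reaction before ipilimumab starts. These lower the chance of an unreviewed re-dose. None of them settles the grade.

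**Conclusion.** The inconsistency is real and narrow. A reaction that resolves, is restarted and recurs meets both the Grade 2 instruction and the printed Grade 3 description, and the two differ on later dosing and reporting. The mandatory criteria in Section 7.4.4 should govern, but the Grade 2 text does not say so.

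The expected count is about 0.2 to 1.0 participants in the whole trial, probably fewer than one. That rests on an assumed 5% to 25% recurrence share, on a rate borrowed from previously untreated patients, and on 96 enrolled rather than treated participants.

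A reader might also infer a threat to the trial's results. The documents do not support that: no endpoint, sample size, error rate or futility rule depends on this text. The edit is worth making because it concerns individual safety and is small.

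**What to change.** In the next amendment, edit Section 7.4.5 in two places.

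1. Keep the sentence "If symptoms recur, then no further study drug will be administered at that visit". It is not limited to one drug, so it bars same-day ipilimumab after a nivolumab recurrence. Add directly after it: *Recurrence after restart meets the Grade 3 description below: manage it under that paragraph, report it to the medical monitor within 24 hours, and, if drug-related, permanently discontinue per Section 7.4.4 (both drugs if attribution cannot be determined).*
2. Begin the Grade 2 premedication bullet with: *For Grade 2 reactions that did not recur after restart.*

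If the sponsor intends a mild recurrence after full resolution to remain Grade 2, one explicit grading sentence in Section 7.4.5 is enough in place of these edits. Sections 7.4.4.1 and 7.4.4.2 act on grade and need no change.

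The cost is two wording edits, with no new procedure or data. The downside of the main option is that a very small number of participants may stop a drug who might otherwise have been re-dosed with premedication.
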